6.4 Dose Delay and Dose Modification

If a patient experiences DLT during the radiation phase or 30 day post radiation observation period the patient will be permanently discontinued from the study.

Maintenance treatment with Alisertib will be repeated every 21 days. In order for a new cycle of therapy to begin, the patient's ANC must be $\geq 1,500/\text{mm}^3$ and the platelet count must be $\geq 75,000/\text{mm}^3$. In addition, any other toxicity considered by the investigator to be related to therapy with Alisertib must have resolved to \leq Grade 1 or to the patient's baseline value before a new cycle of therapy may begin.

If the patient fails to meet the above-cited criteria for retreatment, then initiation of the next cycle of therapy will be delayed for up to 1 week. At the end of that week, the patient will be re-evaluated to determine whether the criteria for retreatment have been met. Should treatment need to be delayed for more than 1 week (i.e., a rest period of more than 21 days) because of incomplete recovery from treatment-related toxicity, the dose of Alisertib will be reduced 1 level when therapy resumes. A second dose reduction may occur should treatment need to be delayed for more than 1 week because of incomplete recovery from treatment-related toxicity on the reduced dosage. Should treatment need to be delayed for more than 2 weeks at any dose, therapy with Alisertib will be discontinued (Table 1).

Dose Level	Dose	Schedule
1	50 mg	PO BID
-1	40 mg	PO BID
-2	30 mg	PO BID
-3	Discontinue	
Level 1 is the standard maintenance dose of 50 mg BID.		

Dose Modifications for Hematological Toxicity

If a patient experiences any of the following hematological toxicities during the dosing period, dosing will be discontinued for the remainder of that cycle and the dose will be decreased 1 level for all subsequent cycles of treatment.

1. _____
2. Grade 4 thrombocytopenia (platelet count $< 25,000/\mu\text{L}$) lasting more than 7 consecutive

days

3. Grade 3 neutropenia with fever or infection, or both, where fever is defined as an oral temperature greater than 38.5°C
4. Grade 3 thrombocytopenia with clinically significant bleeding

If a patient has a platelet count of less than 10,000/ μ l at any time, the patient will be removed from the study permanently.

Hematopoietic growth factors are allowed for febrile neutropenia or prolonged neutropenia, or decided appropriate by the treating physician. The choice of growth factor, dose, and duration is up to the treating physician. CBC should be monitored no less than 2 times a week till the toxicity is resolved to grade 3 or less.

Dose Modifications for Non-hematological Toxicities

If a patient experiences any of the following toxicities during the dosing period, dosing will be discontinued for the remainder of that cycle and the dose will be decreased 1 level for all subsequent cycles of treatment, and treatment may resume after drug related toxicities have resolved to \leq Grade 1 or to baseline.

1. Any Grade 2 or greater neurological toxicity
2. Any Grade 3 non-hematological toxicity that is considered by the investigator to be related to study drug other than:
3. Grade 3 arthralgias/ myalgias
4. Grade 3 or greater nausea or emesis, or both, that occurs in the absence of optimal antiemetic therapy (5-hydroxytryptamine 3 [5-HT₃] serotonin receptor antagonist)
5. Grade 3 or greater diarrhea that occurs in the absence of optimal supportive therapy with loperamide
6. Grade 3 fatigue that lasts greater than 1 week
7. Grade 2 non-hematological toxicities that are considered by the investigator to be related to study drug and in the opinion of the investigator require dose reduction.

In general, Alisertib treatment should be discontinued if a patient experiences a nonhematologic grade 4 toxicity. If, in the opinion of the investigator and study sponsor it is in the patient's interest to continue therapy with Alisertib, then after recovery from the toxicity or toxicities in question to \leq grade 1 or to baseline values, the dose of Alisertib should be reduced by at least 1 dose level with subsequent cycles of therapy.

When a dose reduction of Alisertib is required, no re-escalation of dose will be permitted. If a patient requires more than 2 dose reductions, therapy with Alisertib will be discontinued.

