1.5 Clinical Data to Date

Clinical experience with Alisertib includes phase 1 and 2 studies in both solid tumors and heme-lymphatic malignancies, described below.

Alisertib for clinical studies is being developed in 3 dosage formulations: powder-in-capsule (PIC), enteric-coated-tablet (ECT), and oral solution (OS: for pediatric use). The initial studies employed the PIC formulation, and more recent studies have evaluated safety, PK, relative bioavailability (in reference to the PIC), and antitumor activity after administration of the ECT formulation.

Using the ECT formulation, the dose-escalation, phase 1 portion of an ongoing study, C14007, has evaluated multiple dose levels from 10 to 60 mg BID for 7 days in repeat, 21-day cycles and 50 mg BID has been determined to be the MTD.

In Study C14007, which includes a phase 1 dose escalation using the same ECT formulation employed in this study, multiple dose levels up to 840 mg total cycle dose (60 mg BID for 7 days) were evaluated. At the maximum administered dose of 60 mg BID for 7 days

administered to patients with advanced solid tumors, 3 patients (out of 3 enrolled) developed myelosuppression during the treatment-free period which was considered intolerable and above the MTD of 50 mg BID. In summary, 700 mg total cycle dose (e.g., 50 mg BID administered daily for 7 days) represents the ceiling for dose escalation in these combinations with Alisertib planned for this current study.

The predominant toxicities reflect the mechanism of action in proliferating tissue (bone marrow, GI epithelium, and hair follicles). The suggested management of these toxicities is based on standard clinical paradigms for an anti-proliferative chemotherapeutic agent. Using a treatment-free period for recovery between each cycle of drug administration, the clinical experience from multiple phase 1 through 2 studies indicate that major toxicities can be managed to allow repeat treatment cycles over periods extending beyond 12 months.

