5.2 Treatment Regimen

Alisertib will be administered by mouth, twice daily on days of radiation treatment during the course of FSRT. All patients will receive 10 days of Alisertib, concurrent with 10 daily radiation treatments. The first dose should be administered on the day of, but prior to, the first radiation treatment. The dose of Alisertib will be determined according to the protocol.

During the maintenance therapy period, Alisertib will be administered by mouth, at 50 mg twice daily from day 1 to day 7 of a 21-day cycle. All patients will receive up to 18 cycles, or until tumor progression

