5.3 Risks

Most Common ($\geq 30\%$)

- Nausea, diarrhea
- Decreased number of white blood cells, which may increase risk of infection
- Damaged mucous membranes in the mouth (mouth blisters)
- Decreased number of red blood cells (or anemia) which may cause feelings of tiredness
- Weakness or feeling tired
- Hair loss

Very Common (10% and $<30\%$)

- Pain, including muscle pain, chest pain, and pain from cancer
- Fever with or without decreased white blood cells
- Sleepiness or feeling drowsy
- Bleeding events with or without decreased number of blood platelets
- Cough
- Shortness of breath
- Rash/skin eruption
- Constipation
- Vomiting
- Decrease in weight or loss of appetite
- Fluid retention and swelling (e.g., hands, feet, legs)
- Headache
- Dehydration (decreased body fluids)
- Dizziness

Common ($>1\%$ and $<10\%$)

- Confusion and mental status changes
- Imbalance which can lead to falling
- Anxiety or depression
- Difficulty sleeping

- High or low blood pressure
- Itchy or dry skin
- Bruises
- Inflamed or dry eyes, blurred vision
- Dry mouth
- Difficulty or painful when swallowing, altered taste
- Upset stomach, flatulence
- Difficult or blocked bowel movements
- Hemorrhoids
- Runny nose, sinus or voice problems
- Numbness or tingling in hands or feet
- Abnormal heart rhythm
- Ringing in the ears
- Muscle spasms/weakness
- Fluid around the lungs or abdomen
- Increased sweating or chills
- Abnormal kidney function
- Abnormal liver function test
- Abnormal levels of blood sugar, chemistry, protein or blood clotting time
- Bacterial, fungal or viral infection
- Increased blood bilirubin
- Blood clot (usually in the legs)
- Loss of bladder control

Uncommon (< 1%)

Serious and treatment-related adverse events include: rhabdomyolysis (muscle breakdown that can damage kidneys), bone fracture, blistering skin reaction, multiple organ failure, deafness, shock, hepatic veno-occlusive disease (also known as sinusoidal obstruction syndrome), heart problems, agitation or irritability, and injury to one or more organs that may be life-threatening or fatal.

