 - Grade 3 diarrhea that in the opinion of the Investigator occurs in the setting of inadequate compliance with supportive care measures and lasts for less than 48 hours.
 - Grade 3 dehydration that, in the opinion of the Investigator occurs in the setting of inadequate compliance with supportive care measures and lasts for less than 48 hours.
 - Grade 3 acidosis or alkalosis which responds to medical intervention by returning to \leq Grade 2 within 48 hours.
 - Isolated Grade 3 elevation of liver function tests (LFTs) without associated clinical symptoms, lasting for \leq 14 days in duration.
 - Grade 3 hypocalcemia, hypokalemia, hypomagnesemia, hyponatremia, or hypophosphatemia which responds to medical intervention.
 - Grade 3 hypercholesterolemia.
 - Grade 3 hypertriglyceridemia.
 - Grade 3 alopecia

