Appendix II: Visit Schedule

	Prior to Registration	Pre-treatment	Concurrent phase		Observation phase	Maintenance phase	Recommended Follow up
Time (day)	-14 to -1	-30 to -1	1-7	8-14	Day 13-42	From Day 43 to 1 year	Year 2 and onwards
Informed consent	X						
Demographics	X						
Medical history	X	X					
H & P	X	X	X ⁷	X ⁷	X ⁵	Q 2 months	X ⁶
Neuro exam	X	X	X ⁸	X ⁷	X ⁵	Q 2 months	X ⁶
MMSE		X			X ⁵	Q 2 months	X ⁶
QoL		X			X ⁵	Q 2 months	X ⁶
Vitals		X	X ⁷	X ⁷	X ⁵	Q 2 months	X ⁶
Weight		X	X ⁷	X ⁷	X ⁵	Q 2 months	X ⁶
KP/ECOG	X	X	X	X ⁷	X ⁵	Q 2 months	X ⁶
CBC w diff	X	X	X ⁷	X ⁷	X ⁵	Weekly ³	X ⁶
CMP, Mg +	X	X	X ⁸	X ⁷	X ⁵	Q 2 months	X ⁶
PT/PTT/INR		X					
Lipid Panel			X ⁷	X ⁷	X ⁵	Q 2 months	
EKG		X					
b-HCG	X ⁹						
MRI Brain		X			X ¹	Q 2 months	X ⁶
Treatment:							
RT			X ²	X ²			
MLN8237			X ³	X ³		X ⁴	

Q = every

H & P = History & Physical

NOTE:

1. Brain MRI should be done between days 35-42, then every 2 months for 1st year.
2. RT: daily on weekdays for a total of 10 treatments.
3. Alisertib: BID on days of RT only.
4. Alisertib: 50 mg BID on days 1-7 every 21 days, for up to 18 cycles or until progression.
5. Between day 39 to day 45 (at the end of 30 day observation period), then every 2 months
6. Every 3 months from year 1 to year 2, then every 4-6 months afterwards.
7. All items only need to be done at least once during week 1 and at least once during week 2.
8. Until discontinuation of Alisertib.
9. Pregnancy test should be done within 7 days prior to registration, if applicable

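### Appendix II schedules no chemistry panel before maintenance cycles 2 and 3, although 6.4 makes each cycle depend on resolution of alisertib-related non-haematologic toxicity

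*Combined protocol and SAP*

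**What the plan says.** Section 5.2 gives one maintenance regimen for every cohort: "Alisertib will be administered by mouth, at 50 mg twice daily from day 1 to day 7 of a 21-day cycle", for up to 18 cycles or until progression. Section 1.5 reports, for the same tablet given for 7 days of a 21-day cycle, that "50 mg BID has been determined to be the MTD".

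Section 6.4 sets two conditions for starting a cycle. The first is an ANC and a platelet threshold. The second is that "any other toxicity considered by the investigator to be related to therapy with Alisertib must have resolved to" Grade 1 or lower, or to the patient's baseline. If either condition fails, the cycle is delayed, and longer delays lead to dose reduction or discontinuation.

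The maintenance column of Appendix II, headed "From Day 43 to 1 year", has CBC weekly and CMP/Mg every 2 months. History and physical examination, neurological examination and vital signs are also every 2 months. Footnote 5 places the end-of-observation visit between days 39 and 45, with repeats every 2 months after that. In the concurrent phase, footnote 7 requires items at least once in each of the two weeks, and chemistry is marked in both. No section orders a chemistry panel before a maintenance cycle.

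Section 5.3 lists abnormal liver function tests and abnormal kidney function among the common risks (more than 1% and less than 10%), together with "Abnormal levels of blood sugar, chemistry, protein or blood clotting time".

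**The concern.** The two conditions in 6.4 do not get the same support from the calendar. A weekly CBC means that a count is always available when a cycle is due. The second condition covers all other related toxicity, and part of that can be seen only in a laboratory result. Section 8.2 requires questioning about adverse events at each contact, and examination as appropriate. That should pick up symptomatic and most neurological toxicity, but not a raised transaminase, a falling creatinine clearance or an electrolyte shift in a patient who feels well.

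A site could therefore follow Appendix II exactly and re-dose at the single-agent MTD over an abnormality that 6.4 would have used to delay the cycle or, at Grade 3, to reduce the dose. The same abnormality could go unrecorded, although safety and tolerability of the study treatment is a primary objective (2.1) and adverse events are reportable until 30 days after the last treatment (8.1). Chemistry is checked at least weekly during the two concurrent weeks and then drops to every 2 months in maintenance.

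**Working it through.** The plan states no figure for this point, so the check compares calendar days.

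**Inputs**
- Maintenance starts on day 43 (Appendix II column heading).
- The cycle length is 21 days, with dosing on days 1-7 (5.2, 6.4).
- The end-of-observation chemistry falls on day f, with f = 39 to 45 (footnote 5).
- Later chemistry comes every 2 months. Assumption: s = 56 to 61 days.
- Assumption: no cycle delays.
- There are 7 values of f and 6 of s, so 42 combinations.

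**Cycle starts and dosing blocks.** Start of cycle k = 43 + 21(k − 1).

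| Cycle | Start (day) | Dosing block (days) |
|---|---|---|
| 1 | 43 | 43-49 |
| 2 | 64 | 64-70 |
| 3 | 85 | 85-91 |
| 4 | 106 | 106-112 |
| 5 | 127 | 127-133 |
| 6 | 148 | 148-154 |

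**Scheduled chemistry**
- First panel: day 39-45.
- Second panel, f + s: from 39 + 56 = 95 to 45 + 61 = 106.
- Third panel, f + 2s: from 39 + 112 = 151 to 45 + 122 = 167.

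**Is there a scheduled panel between the end of one block and the next start?**
- Before cycle 2 (days 50-64): none in any of the 42 combinations. The latest panel is 64 − 45 = 19 to 64 − 39 = 25 days old. It was drawn before cycle 1 or in the first days of its block.
- Before cycle 3 (days 71-85): none in any combination. The latest panel is 85 − 45 = 40 to 85 − 39 = 46 days old.
- Before cycle 4 (days 92-106): one in all 42, at 106 − 106 = 0 to 106 − 95 = 11 days before the start.
- Before cycles 5 and 6 (days 113-127 and 134-148): none, because the third panel is on day 151 at the earliest.

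So 2 of the first 4 cycle starts, and 4 of the first 6, have no scheduled chemistry after the preceding dosing block. By the second panel, three blocks are complete: 3 × (50 mg × 2 × 7) = 3 × 700 = 2,100 mg.

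**Sensitivity to delay.** A single one-week delay moves cycle 3 to day 92, still before day 95. Longer or repeated delays could bring a panel in ahead of cycle 3 for some combinations.

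**Patients.** If the range in 5.3 applied to all 24 possible subjects, each listed abnormality would be expected in 24 × 0.01 = 0.24 to 24 × 0.10 = 2.4 of them. That counts any grade, with or without symptoms, and not every subject will reach maintenance. The quantity of interest (symptom-free, related, Grade 2 or higher) would be smaller, and the documents do not give it.

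**The case against.** The strongest reply is that 6.4 governs toxicity already recognised and attributed by the investigator. It is not a screening order, and nothing stops the investigator from ordering chemistry. On this view 6.4 and Appendix II do not contradict each other; the calendar simply sets a lower test frequency. That fits the toxicity profile: 1.5 names marrow, gastrointestinal epithelium and hair follicles as the main targets, and the numbered risk list in 1.6 has no hepatic or renal entry. This much stands: the tests are not scheduled, which is different from saying that the toxicity cannot be checked, and there is no outright contradiction. But an abnormality must be found before it can be attributed, and a silent one gives no reason to look.

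Footnote 8, "Until discontinuation of Alisertib", might be read as continued chemistry. It is attached to week-1 cells and gives no frequency, while the maintenance cell states every 2 months without it. The superscripts are not fully reliable either: the weekly CBC cell points to footnote 3, which concerns dosing on radiation days. If continued testing was intended, the calendar needs to say so.

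A reader might also infer three stronger points, which the documents do not support:
- **That the plan predicts silent liver toxicity.** Section 6.2 mentions "Isolated Grade 3 elevation of liver function tests (LFTs) without associated clinical symptoms", but as an exception to the DLT definition. It says what would not count, not what will occur. The support is the list in 5.3, which gives neither grade nor symptom status.
- **That lower cohorts face a steep dose step in maintenance.** A 10 mg BID patient would go to five times the single dose, but that ignores 10 concurrent dosing days against 7. A 40 mg BID patient has already taken 40 × 2 × 10 = 800 mg against 700 mg per maintenance block. For 30 mg the ratio is 700/600 = 1.17, and for 20 mg it is 700/400 = 1.75. The 10 mg level is used only if 20 mg BID proves too toxic.
- **That cycles 17 and 18 fall outside the schedule.** They would start on days 379 and 400, with the last dose on day 406. If the year runs from day 1, the column ends before them and footnote 6, "Every 3 months from year 1 to year 2, then every 4-6 months afterwards", takes over. If it runs from day 43, it ends on day 43 + 365 = 408 and covers them. The text does not settle which, and the footnote problem adds to the doubt.

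**Conclusion.** The point holds as a scheduling gap. A site that follows Appendix II starts cycles 2 and 3 with no scheduled chemistry after any completed maintenance block, in all 42 combinations examined, and the next panel comes after three blocks. This rests on maintenance starting on day 43, no delays, and 2 months meaning 56-61 days.

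The counts are gaps in the calendar, not missed toxicities. How many patients would be affected is unknown and probably small. It would be wrong to infer that dose escalation is compromised: DLTs are counted only during radiation and for 30 days afterwards (6.2, 6.3), so DLT and MTD decisions are untouched. What is at stake is patient safety and complete toxicity reporting in maintenance. The change is a cheap improvement that should be made.

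**What to change.** In the maintenance column of Appendix II, add CMP/Mg to the weekly CBC draw nearest before day 1 of every cycle, for as long as alisertib is given. State in 6.4 that the result is reviewed against the retreatment criteria before dosing. Correct the footnotes on the chemistry and CBC rows so that they agree with this.

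The cost is a calendar amendment and at most one extra panel per cycle on a draw that is already scheduled, with none added where a 2-monthly panel already falls in that week.

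### Section 6.4 does not define the dosing period: read as days 1–7, one maintenance haematological trigger cannot be met and rest-period events do not count

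*Combined protocol and SAP*

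**What the plan says.** Section 5.2 (also Section 1.3.2 and Appendix II, note 4) gives maintenance alisertib "at 50 mg twice daily from day 1 to day 7 of a 21-day cycle", for up to 18 cycles or until progression.

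The haematological part of Section 6.4 opens with: "If a patient experiences any of the following hematological toxicities during the dosing period, dosing will be discontinued for the remainder of that cycle". The dose then also drops one level for all later cycles. The listed triggers are:

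- item 1, which is blank in the text supplied and cannot be assessed;
- item 2, Grade 4 thrombocytopenia "lasting more than 7 consecutive" days;
- item 3, "Grade 3 neutropenia with fever or infection, or both";
- item 4, "Grade 3 thrombocytopenia with clinically significant bleeding".

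Two other rules in Section 6.4 are not confined to the dosing period. A cycle may start only with ANC of at least 1,500 and platelets of at least 75,000 per mm³. A delay of more than 1 week for incomplete recovery brings a one-level reduction, and a delay of more than 2 weeks brings discontinuation. Separately, for platelets below 10,000 "at any time, the patient will be removed from the study permanently".

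On timing, Section 1.5 states that 3 of 3 patients given 60 mg twice daily for 7 days "developed myelosuppression during the treatment-free period which was considered intolerable".

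**The concern.** The reduction rule looks for toxicity in a period that the protocol does not define. If that period is the seven days on drug, the rule has two problems. One of its triggers lasts longer than the window in which it must occur. The window also leaves out the drug-free days, which is where the protocol's own clinical summary places myelosuppression.

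Consider a maintenance patient with febrile Grade 3 neutropenia on day 12 whose counts and other toxicity recover by the next due date. Read literally, neither the reduction rule nor the delay rule acts, and the next cycle starts at the same dose. A physician who takes the rule to cover the whole cycle would reduce. At this single center, the same event could therefore be handled differently by different treating physicians or at different times. The situation can recur over up to 18 cycles, and Section 6.4 does not allow re-escalation after a reduction.

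**Working it through.** **Do the documents themselves treat days 8–21 as rest?** Two of their own figures were reproduced.

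- The delay rule in Section 6.4 equates a delay of more than 1 week with a rest period of more than 21 days. Cycle length minus dosing days plus delay is (21 − 7) + 7 = 21 days. This works only if days 8–21 count as rest.
- Section 1.5 gives total cycle doses of 700 mg and 840 mg: 50 × 2 × 7 = 700 and 60 × 2 × 7 = 840. Both confirm seven dosing days.

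The consequence attached to the triggers points the same way. Stopping the remaining doses of a cycle has meaning only while doses remain, that is, up to day 7.

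**Can item 2 be met in days 1–7?** More than 7 consecutive days means at least 8 in whole days. A Grade 4 platelet count (below 25,000) cannot be carried into day 1, because 75,000 is needed to start the cycle. For onset on day *o* and duration *d*, the spell fits if *o* + *d* − 1 ≤ 7. The smallest case is *o* = 1, *d* = 8, giving 8 > 7, so no spell fits. The condition is first met on day 8 for onset on day 1, and on day 14 for onset on day 7. Both fall after the last dose of the cycle.

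**How the result depends on the reading**

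| Reading of dosing period | Item 2 | Items 3 and 4 on days 1–7 | Items 3 and 4 on days 8–21 |
|---|---|---|---|
| Event falls within days 1–7 | never met | count | do not count |
| Event starts in days 1–7 | can be met from day 8 | count | do not count if onset is after day 7 |
| Whole cycle | can be met from day 8 | count | count |

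On the second and third readings, no doses are left to stop once item 2 is met. Only the reduction for later cycles has any effect.

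**Does the delay rule catch what the window leaves out?** Take item 2 with onset in the rest period and *d* ≥ 8. Assume the retreatment threshold is reached on day *o* + *d*.

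- Next cycle on time (day 22): *o* + *d* ≤ 22, so *o* ≤ 14. Onsets on days 8–14 can recover with no delay.
- Delay of 1 week at most (day 29): *o* + *d* ≤ 29, so *o* ≤ 21. Onsets on days 8–21 can recover without a delay of more than 1 week.

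Neither case leads to a reduction under either rule. These are outer limits: each extra day needed to climb from Grade 4 to 75,000 moves the latest onset one day earlier. Items 3 and 4 have no duration condition, so they escape more easily, as in the day-12 example. The removal rule for platelets below 10,000 covers a more extreme platelet event and no neutropenia.

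**How many events would be missed?** The calendar share outside the window is 14/21 = 67%, but this is not a share of events. The timing evidence is 3 of 3, for which the exact two-sided 95% lower limit is 0.025^(1/3) = 29.2%. It was seen at 60 mg, not 50 mg, and no grade or duration is given. If a share *q* of item 3 and 4 events arises in the rest period, the rule read as days 1–7 catches at most 1 − *q* of them. The documents do not give *q* at 50 mg, and it could lie anywhere from 0 to 1.

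**The case against.** The strongest reply is that days 1–7 is an inference. The authors of item 2 evidently expected it to be assessable for longer than a week, which suggests loose drafting. On an onset or whole-cycle reading, item 2 can be met. This stands as far as it goes, and it rules out any claim that the narrow window was deliberate. It also confirms that the term needs a definition, because the three readings lead to different actions for the same patient.

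A second reply is that retreatment thresholds, the delay-based reduction, the platelet removal rule and investigator withdrawal for an unacceptable adverse event (Section 4.5.1) protect the patient. They do narrow the gap. They do not supply a reduction when the patient recovers in time.

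Several stronger readings are tempting but not supported:

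- A reader might infer that the reduction rule as a whole rarely or never fires. That is shown only for item 2. Items 3 and 4 can fire on days 1–7, and item 1 cannot be judged.
- A reader might take the 3 of 3 patients as the expected pattern in maintenance. They received a dose above the stated single-agent MTD, and the report does not show that they met items 2–4 or that events during dosing are rare.
- A reader might expect differences between sites, or a distorted dose-intensity endpoint. The study is single-center, and no such endpoint is defined.

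**Conclusion.** The point holds as an internal inconsistency in a safety rule. The dosing period is undefined. Read as days 1–7, item 2 is impossible to meet, and item 3 and 4 events on 14 of the 21 cycle days are disregarded. Rest-period events that recover without a delay of more than 1 week lead to no dose reduction under either the reduction rule or the delay rule.

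This rests on the day 1–7 reading, which Section 5.2, the 21-day rest figure and the consequence clause all support but no definition confirms. The frequency of affected events at 50 mg twice daily cannot be computed from the documents.

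A reader might infer that the MTD is at risk. It is not: Section 6.3 sets the toxicity assessment period at 30 days after radiation, and maintenance starts only after that. The inconsistency bears on patient safety and consistent handling in maintenance and should be reconciled. It is not an error in the primary MTD determination.

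**What to change.** Define *dosing period* in Section 6.4 and reconcile that section with Section 5.2 (the 7-day schedule) and Section 1.5 (timing of myelosuppression). The stated window and the listed duration conditions should be consistent with each other. The text should also say how an event in the treatment-free period is handled when the next cycle is due.

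Apply the same check to the non-haematological list in Section 6.4. It uses the same phrase and includes Grade 3 fatigue persisting beyond 1 week. The numbering in the supplied text does not make clear whether that item is a trigger or an exception, but in either role its duration cannot be completed in seven days.

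Which window and which clinical rule apply is for the investigators and sponsor to decide.

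The cost is a short wording amendment. Appendix II already schedules weekly blood counts in maintenance, so defining the term adds no tests. Depending on the window chosen, somewhat more dose reductions may be recorded.

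### In section 6.4 the Grade 3 fatigue item most naturally reads as sparing prolonged related fatigue the dose reduction that shorter fatigue requires

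*Combined protocol and SAP*

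**What the plan says.** The non-hematological part of section 6.4 (Dose Delay and Dose Modification) lists events which, if they occur in the dosing period, end dosing for that cycle and lower the dose one level from then on. Item 1 is neurological toxicity of Grade 2 or worse. Item 2 is any Grade 3 non-hematological toxicity "considered by the investigator to be related to study drug other than", followed by a colon. The numbering then runs on unbroken:

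- Item 3: arthralgia or myalgia.
- Item 4: nausea or emesis without optimal antiemetics.
- Item 5: diarrhea without optimal loperamide.
- Item 6: "Grade 3 fatigue that lasts greater than 1 week".
- Item 7: related Grade 2 toxicities that "in the opinion of the investigator require dose reduction", which is plainly a trigger again.

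The maintenance levels are 50, 40 and 30 mg BID, then discontinuation. The section adds: "When a dose reduction of Alisertib is required, no re-escalation of dose will be permitted". It also states: "If a patient requires more than 2 dose reductions, therapy with Alisertib will be discontinued".

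Before retreatment, related toxicity must be back to Grade 1 or less, or to the patient's "baseline value before a new cycle of therapy may begin". A delay of more than 1 week for unresolved related toxicity brings a one-level reduction, and a delay of more than 2 weeks ends therapy.

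**The concern.** Items 3 to 5 make sense only as exceptions to item 2. Item 6 comes straight after them, and related Grade 3 fatigue is a subset of what item 2 covers, so the reader's first inference is that item 6 is also an exception. The rule then runs backwards: the longer episode is excused and the shorter one is penalized.

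Two clinicians could dose the same patient differently. One patient with a long episode that recovers in time may restart at the unchanged dose. Another with a short episode loses a level for good and uses one of two permitted reductions. At 30 mg BID the short episode ends therapy, while the long one need not.

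Fatigue is a foreseeable event here. Section 1.6 names it as a risk, and section 5.3 puts weakness or tiredness among effects seen in 30% or more of patients. That figure is not specific to Grade 3.

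**Working it through.** The plan gives no figure on this point, so the check sets out the rule under each reading.

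**Step 1. Mandatory reduction under this list, by reading.** Durations above 7 days assume recovery in time for retreatment (step 3).

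| Grade 3 fatigue | Duration (days) | Item 6 as exception | Item 6 as separate trigger |
|---|---|---|---|
| Related | 3 or 7 | Reduce | Reduce |
| Related | 8, 14 or 20 | No reduction | Reduce |
| Not related | 3 or 7 | No reduction | No reduction |
| Not related | 8, 14 or 20 | No reduction | Reduce |

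As an exception, item 6 inverts the rule for related fatigue. As a trigger, its 1-week limit changes nothing for related fatigue, because item 2 already covers every duration. The limit then bears only on fatigue not judged related.

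**Step 2. How the protocol treats duration elsewhere.** Sections 6.2 and 6.4 contain eight other duration-limited toxicity items. The blank first item in the hematological list is not counted.

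- Five are exceptions that excuse the shorter event, all in section 6.2: nausea or vomiting, diarrhea, and dehydration, each under 48 hours; acidosis or alkalosis improving within 48 hours; isolated liver test elevation of 14 days or less.
- Three are triggers that catch the longer event: Grade 4 neutropenia of 7 days or more and persistent Grade 3 electrolyte events (section 6.2), and Grade 4 thrombocytopenia "lasting more than 7 consecutive" days (section 6.4).

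All 8 of 8 treat the longer event as the worse one. Item 6, read as an exception, would be the only one reversed.

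**Step 3. Timing.** Section 5.2 sets maintenance dosing on days 1 to 7 of a 21-day cycle. I take the dosing period to be those days and the next cycle to be due on day 22.

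- Fatigue starting on day d reaches 7 days on day d + 7. That is day 8 for d = 1 and day 14 for d = 7, so always after the last dose.
- Days left before the next cycle: 22 − 8 = 14 and 22 − 14 = 8. The duration is therefore known before the next dose is set.
- Longest episode with no delay: 22 − 1 = 21 days (onset day 1) and 22 − 7 = 15 days (onset day 7).
- With a 1-week delay the restart is day 29, and the rest period is 14 + 7 = 21 days, which matches section 6.4's own gloss. The longest episodes are 29 − 1 = 28 and 29 − 7 = 22 days.

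These are times to recovery to Grade 1 or baseline, so the Grade 3 part may be shorter.

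**Step 4. Dose at stake.** Cycle doses are 50 × 2 × 7 = 700 mg, 40 × 2 × 7 = 560 mg and 30 × 2 × 7 = 420 mg. One level down costs 1 − 560/700 = 20% from the top, or 1 − 420/560 = 25% from the middle. Below 30 mg BID the table says to discontinue. On the exception reading the longer episode may carry none of this.

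**The case against.** The strongest reply is that the inversion depends on layout that cannot be seen. If item 6 stood level with item 2 in the source, it is a trigger and nothing is reversed. That reading is coherent: item 1 also has no relatedness test, and a rule that does not depend on attribution has some use, since section 1.5 says the cause of CNS effects was sometimes confounded. This stands, so a reader should not infer that the protocol certainly inverts the rule. It does not settle the matter, because the text as given does not mark where the exceptions end, and the trigger reading leaves the limit redundant for related fatigue.

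A second reply is that new related Grade 3 fatigue meets item 2 at onset, before it can have lasted a week. The stop and the reduction are then already triggered, and restarting at the same dose means cancelling that reduction, a step the text does not describe. This also stands. The within-cycle stop is safe on either reading. The harm arises only if the clinician applies the exemption when setting the next cycle's dose.

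Third, seven of the eight comparison items come from the DLT definitions, which serve a different treatment phase. The count shows the protocol's usage and no more. It also suggests that some clinicians would reject the reversed reading.

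**Conclusion.** The point holds as a minor drafting fault with a dosing consequence. On its most natural reading, item 6 excuses prolonged related Grade 3 fatigue from the mandatory reduction while shorter fatigue incurs it. On the other reading there is no inversion, only a limit that is redundant for related fatigue.

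The effect is confined to maintenance patients whose fatigue lasts over 1 week and recovers by day 22, or by day 29 with a delay of 1 week or less. This rests on the dosing period being days 1 to 7 and on duration being judged before the next cycle.

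Two stronger inferences are not supported:

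- *Prolonged fatigue goes unmanaged.* Recovery before retreatment, the delay-based reduction and discontinuation, discretionary reduction for Grade 2 events, and withdrawal for an unacceptable adverse event (section 4.5.1) all remain. None of them, though, restores a mandatory reduction for an episode that recovers in time.
- *Dose finding is compromised.* The DLT, 3+3 and MTD rules are untouched.

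How many patients are affected is unknown, because no Grade 3 fatigue rate or duration is given. The enrollment limit of 24 is only a ceiling, and patients with a DLT leave before maintenance.

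**What to change.** Nest items 3 to 5 under item 2 as its exceptions and keep item 7 as a separate trigger. State that related Grade 3 fatigue of any duration stops dosing for the rest of the cycle, and that related Grade 3 fatigue over 1 week always brings the one-level reduction for later cycles. The sponsor should then choose one of two treatments of short fatigue.

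- **Excuse it.** Exempt Grade 3 fatigue lasting 1 week or less from the dose reduction only, not from the within-cycle stop, and judge duration at the existing retreatment check. In the step 1 table, related fatigue of 3 or 7 days then brings no reduction, and 8, 14 or 20 days does. The small downside is that short related Grade 3 fatigue, which forces a reduction on either current reading, no longer would.
- **Do not excuse it.** List item 6 as a separate trigger level with item 2. This removes the inversion and relaxes nothing. The 1-week limit would then act only on fatigue not judged related, which the sponsor should accept knowingly.

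Either choice costs a change in list level and a sentence or two, with no new visits or data.
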